8.5.2	KNOWN POTENTIAL BENEFITS	ERROR! BOOKMARK NOT DEFINED.
8.5.3	ASSESSMENT OF POTENTIAL RISKS AND BENEFITS	ERROR! BOOKMARK NOT DEFINED.
9.	LIST OF REFERENCES	27

Summary of Changes from Previous Version

Date of submission	Summary of Revisions Made	Rationale for modification	Approval date
02-09-21	Randomization changed to tertiles of sessions practiced per week	Based on a review of current practice patterns for our providers, stratifying based on number of sessions that a physician practices per week (which is proportional to panel size) is a more practical and predictable measure to use prospectively (since number of sessions per week changes less than visit volumes). Further, tertiles of panel size will be easier to implement with a 3-arm trial than quintiles. The intent of stratification is the same, but our proposed change will be easier to operationalize.	02-18-21
02-09-21	Inclusion/exclusion criteria	To ensure that we enroll only actively-practicing outpatient providers who are able to receive weekly interventions and who care for a sufficient volume of patients, we propose to exclude providers who practice less than one session per week or whose total panel size is less than 100 patients.	02-18-21
02-09-21	Revisions of interventions	We have shortened the text in the two interventions to make it easier and faster for providers to read (social norming, academic e-detailing)	02-18-21
06-02-21	Revision of intervention frequency	We have altered the frequency with which we send out the dashboard component of the social norming intervention from weekly to every 2-4 weeks. This frequency will more accurately reflect the rate of change of the percentage of uncontrolled hypertensive patients among PCPs.	
09-28-21	Revision of inclusion/exclusion criteria Revision of goal blood pressure Addition of subject lines to intervention messages Changed sample size determination calculations Modified study timeline	To ensure we have a large enough pool of participants to draw from, we have altered the study timeline and the eligibility criteria of providers to include those with at least 2 patients meeting the eligibility criteria, instead of the original requirement of at least 10. Additionally, we have modified our blood pressure goal to be <140/90 for all patients to streamline identification of eligible patients. Finally, we have modified our sample size and power calculations to allow us to detect a larger effect size.	

1. Background and Rationale

Hypertension is a large contributing factor to cardiovascular morbidity and mortality among older adults, yet more than half of patients with hypertension have blood pressures above clinical goal.¹ The failure of physicians to initiate or intensify treatment regimens when clinically indicated is often referred to as clinical inertia, and is a well-described phenomenon in the treatment of this condition.²⁻⁵

Interventions to reduce clinical inertia and improve blood pressure control, including education, reminders, feedback, ambulatory blood pressure monitoring, and pharmacist-driven interventions, have been shown to be effective but only modestly so.⁵ One hypothesis for this limited effectiveness is that physicians may have different underlying behavioral factors that contribute to their inertia behavior. A qualitative analysis of cases of clinical inertia in hypertension care identified seven distinct categories of physician justifications for non-intensification.⁶

Behavioral science research suggests that individuals are influenced by factors of which they are not consciously aware. When describing reasons for their own behavior, people generally over-value personal introspection rather than context^{7,8} and generate explanations of their behaviors to help resolve cognitive dissonance or the discomfort of an “explanatory vacuum”.⁹ In the case of inertia, multiple and/or variable underlying behavioral tendencies, such risk aversion, conscientiousness, burnout, or need for closure, are likely more relevant explanations for physician behavior than physician-provided justifications. Thus, rather than relying on justifications, an alternative approach is to measure behavioral factors through surveys and empirically elucidate which physician behavior characteristics are correlated with clinical inertia and with a physician’s responsiveness to different interventions intended to address this problem.

Further, physicians are likely influenced by context and may behave differently with different patients. For example, a physician may not intensify treatment with a healthy patient who strongly prefers to try diet/exercise, but that same physician might consider blood pressure values that are just a few points higher than goal to be “close enough” for older patients that have many comorbidities.

Accordingly, we propose to measure physician behavioral factors using survey instruments, test interventions for clinical inertia in hypertension care, and identify characteristics of patients and

physicians that are associated with the likelihood of treatment intensification and their responsiveness to different interventions. This information could then be used to more effectively design and target interventions to those most likely to respond.

2. Study Aims

The main aims are to 1) test two interventions to reduce clinical inertia in hypertension prescribing compared to control and 2) develop a model to predict intervention responsiveness based on physician and patient characteristics.

The objectives and endpoints for this project are summarized below.

OBJECTIVES	ENDPOINTS	JUSTIFICATION FOR ENDPOINTS
Aim 1		
To determine the effectiveness of two interventions to reduce hypertension clinical inertia compared to control	Primary: Intensification of hypertension treatment medications (i.e. dose increase or medication addition) at the time of the patient's visit Secondary: Mean change in systolic blood pressure in each intervention group compared to control over 6 months	These outcomes are directly related to the interventions, are clinically meaningful, and are measurable using routinely collected data in the Electronic Health Record (EHR)
Aim 2		
To identify patient and physician clusters and determine association of those clusters with intervention responsiveness	Characteristics of patient and physician predictors that are associated with 1) clinical inertia in HTN care and 2) intervention responsiveness	A model predicting intervention responsiveness could be used to tailor future interventions specifically to physicians in order to increase intervention effectiveness

3. Study Design

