3.2.1 Aim 1 Design

In Aim 1 of the study, we will conduct a three-arm randomized controlled trial to compare the effectiveness of two interventions compared to control on clinical inertia in hypertension treatment. We will recruit 45 primary care physicians (PCPs) in the Mass General Hospital (MGH) system caring for patients who are potentially in need of hypertension treatment intensification.

Using EHR data, we will first identify patients: (1) aged 18-79; (2) for whom the recent blood pressure (BP) history in the last 18 months is above goal, (3) whose most recent BP at an outpatient visit was above goal, and (4) who did not have their hypertension treatment regimens intensified (dose increase, new medication added, or medication exchange) at or since that time.

The BP goal for this study will be <140/90 for all patients. If there are multiple blood pressures on the same day, we will select which BP to use for the study. This will either be the lowest BP from that day (if this is routinely available in the EDW) or the last BP measured that day (this is available in the EDW). The choice of which BP to use will be applied uniformly to all patients after reviewing preliminary data on BP availability in the EDW. To accommodate changes in care delivery that occurred during the COVID surge, outpatient visits will include in-office and virtual visits that had vitals recorded in the EHR the same day. We will exclude patients who,

based upon EHR data, are excluded from the hypertension registry, are pregnant or post-partum 6 months, or who are receiving hospice care.

In order to ensure that sufficient patient visits occur during the intervention period for Aim 1 and enough patients per physician for our prediction model development in Aim 2, primary care physicians will need to have at least 2 patients on their panel meeting these criteria to be eligible for the study. We will also exclude physicians with fewer than 100 patients on their primary care panel or who practice less than 1 session per week.

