6.2 Outcomes

The *primary outcome* will be whether physicians intensified treatment at the visit targeted by the intervention. Intensification of treatment will include an increase in dose of an existing antihypertensive medication, adding an additional medication, or rotation of one medication to another that is stronger or more appropriate for the patient (e.g. changing hydrochlorothiazide to furosemide for a patient with chronic kidney disease). These will be measured using prescribing information from the EHR on the day of the patient's visit.

The *secondary outcome* will be the change in systolic blood pressure over 6-months of follow-up in each intervention arm compared to control. The initial value will be the systolic blood pressure at the time of enrollment that determined the patient's eligibility for participation. The follow-up blood pressure will be the last blood pressure available in the EHR within 6 months after the visit targeted by the intervention. Based on prior studies in a similar local healthcare system, we anticipate approximately 20% missingness rate for the follow-up blood pressure within 6 months, and that this will likely be non-differential between treatment arms.²⁵ Should there be sufficient missing data (e.g., >10%), we will use multiple imputation to handle this. In specific, we will use 20 imputations with Proc MI in SAS to impute any estimated values using fully conditional specification. Analyses will then be conducted on each imputed dataset and combined using Rubin's rules.²⁶ We will perform a complete case analysis as a sensitivity analysis.

Each post-intervention interview will be moderated by trained study staff using a semi-structured interview guide that asks physicians about barriers to hypertension treatment intensification, perspectives on different intervention arms, and suggestions for improvement.

We will use results from the physician interviews and study staff expertise to select variables for inclusion in the predictive modeling analysis. These variables will all be available in either the EHR or baseline physician surveys and will include, but are not limited to: physician age, gender,

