7.3 Statistical analyses

7.3.1 *Analysis of the primary endpoint*

The primary outcome of this trial will be whether physicians intensified treatment at the visit targeted by the intervention. These data will be collected through EHR data from MGB. We will evaluate the primary outcome using generalized estimating equations (GEE) to adjust for provider-level clustering and multiple patient observations per physician with a logit link function and binary distributed errors; these models will also adjust for the block-randomized design. Because this is a randomized trial, our primary analyses are planned as unadjusted; however, if there are strong predictors of the outcomes not balanced by block randomization, we will adjust for these in the primary analyses. We will conduct analyses using intention-to-treat principles and each intervention arm will be compared to control. Given the nature of the data and how the outcome is being measured, there should not be missing values for our primary outcome.

7.3.2 *Analysis of secondary endpoints*

The secondary outcome of this trial is change in systolic blood pressure control in each arm over 6 months. For this secondary outcome, we will use GEE with an identity link function and normally-distributed errors to account for provider-level clustering, adjusting for the block-randomized design. As in the primary analysis, we will perform analyses unadjusted and adjusted for provider and patient-level covariates to accommodate any imbalance across arms. We will conduct analyses using intention-to-treat principles and each intervention arm will be compared to control. Based on prior studies in a similar local healthcare system, we anticipate approximately 20% missingness rate for the follow-up blood pressure within 6 months, and that this will likely be non-differential between treatment arms.²⁵ Should there be sufficient missing data (e.g., >10%), we will use multiple imputation to handle this. In specific, we will use 20 imputations with Proc MI in SAS to impute any estimated values using fully conditional specification. Analyses will then be conducted on each imputed dataset and combined using Rubin's rules.²⁶ We will perform a complete case analysis as a sensitivity analysis.

7.3.3 *Baseline descriptive analyses*

We will report the means and frequencies of baseline variables for physicians and their eligible patients.

7.3.4 *Subgroup analyses*

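### The secondary systolic BP outcome is a raw change from one reading selected for being high: the 6-month label, the within-arm changes and the precision suffer, but the contrast with control is not biased

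*Combined protocol and SAP*

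**What the plan says.** The endpoints table in section 2 gives the secondary endpoint as "Mean change in systolic blood pressure in each intervention group compared to control over 6 months". Section 6.2 defines its two ends:

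- Start: "The initial value will be the systolic blood pressure at the time of enrollment that determined the patient's eligibility for participation".
- End: "The follow-up blood pressure will be the last blood pressure available in the EHR within 6 months after the visit targeted by the intervention".

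Section 3.2.1 shows how the starting value is selected. Patients are those "for whom the recent blood pressure (BP) history in the last 18 months is above goal" and "whose most recent BP at an outpatient visit was above goal", and "The BP goal for this study will be <140/90 for all patients". No recency limit is set for the qualifying reading itself. Where a day has several readings the choice is still open: "This will either be the lowest BP from that day", or the last one.

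For the analysis, section 7.3.2 says "we will use GEE with an identity link function and normally-distributed errors to account for provider-level clustering", with adjustment for the block-randomised design and comparison of each intervention arm with control. Unadjusted and adjusted versions are planned. The adjusted version is there to deal with imbalance, and its covariates are not listed. Section 6.1 collects baseline systolic BP, but 7.3.2 does not name it as a covariate. Regression to the mean is not mentioned.

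**The concern.** There are three consequences.

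1. **The label.** The 6 months runs from the targeted visit to the follow-up reading. The change runs from the qualifying reading, which is earlier by an amount the plan does not limit or propose to report.
2. **Within-arm changes.** A reading kept because it was high contains some chance elevation, which disappears at the next measurement without treatment. Section 7.3.2 opens by describing the outcome as change in each arm, which invites a reader to take the arm-level falls as results. Section 7.2 says the trial is meant to inform larger evaluations, so a control-arm fall misread as real could carry into later planning.
3. **Precision.** Subtracting one noisy reading in full carries its noise into every patient's score. A model that estimates the coefficient of baseline does better, and one that uses several earlier readings does better again. Those readings lie in the BP history that eligibility already draws on.

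**Working it through.** The documents give no SD, correlation, target difference or power for systolic BP, so there is no stated figure to reproduce. All SDs and correlations below are assumptions.

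**Step 1. The interval.** Span = age of the qualifying reading + wait to the targeted visit + time to the last follow-up reading.
- Age: up to 18 months, by implication only, because 3.2.1 attaches the window to the BP history.
- Wait: up to 6 months if eligibility is fixed at study start (3.6 allows up to 6 months of intervention), or only weeks if lists are refreshed as 5.2 suggests.
- Follow-up: up to 6 months (6.2).

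Outer bound: 18 + 6 + 6 = 30 months with fixed eligibility, or about 18 + 6 = 24 months with refreshed lists. Only the last term is the labelled 6 months.

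**Step 2. The artificial fall.** For normally distributed readings selected on one value, expected fall = (1 − rho) × (mean of selected readings − population mean).
- Population mean 135, SD 18, rho 0.6, selection at 140 or above: the selected mean is 152.7, so the fall is 0.4 × 17.7 = 7.1 mmHg.
- Over means 135 or 145, SD 15 or 18 and rho 0.4 to 0.7, simulation gives 2.7 to 10.6 mmHg. If earlier readings must also average 140 or more, it gives 1.8 to 8.3 mmHg.
- A second model (usual mean 134, between-patient SD 10 to 13, visit-to-visit SD 10 to 12, with and without drift) gives about 5 to 11 mmHg.
- Age matters. With mean 135, SD 18, rho 0.6 and one earlier high reading, the fall is 4.9 mmHg and the SD of change 14.9. If the true level at the qualifying reading correlates only 0.8 with that at follow-up, these become 7.9 and 16.8.

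With no treatment effect the fall is the same in every arm, so the expected difference from control is 0.

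**Step 3. Precision.** Inputs borrowed from 7.2: 15 physicians × 12 patients = 180 per arm, and ICC 0.05 (given there for the binary primary outcome). Design effect = 1 + 11 × 0.05 = 1.55.

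95% CI half-width = 1.96 × SD × √(2 × 1.55/180) = 0.257 × SD.

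Example (usual mean 134, between-patient SD 12, visit-to-visit SD 12, three readings, last reading and window mean both 140 or more):

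| Analysis | Half-width, mmHg | Implied SD (half-width/0.257) |
|---|---|---|
| Raw change from qualifying reading | 3.99 | 15.5 |
| Follow-up adjusted for qualifying reading | 3.65 | 14.2 |
| Raw change from window mean | 3.48 | 13.5 |
| Follow-up adjusted for window mean | 3.45 | 13.4 |

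Full gain: (3.99 − 3.45)/3.99 = 13.5%. Share from adjusting for the qualifying reading alone: (3.99 − 3.65)/(3.99 − 3.45) = 0.34/0.54 = 63%. This share varies with the SDs and the number of readings.

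**Step 4. Range.**
- Without drift, adjusting for the window mean cuts variance by 20 to 30% against raw change. In half-width this is 1 − √0.80 = 10.6% to 1 − √0.70 = 16.3%.
- Drift, or a regimen change within the window, lowers the gain. Over all scenarios roughly 7 to 15% is a fair summary.
- In the first model of Step 2, the variance of raw change is 1.05 to 1.26 times that of the analysis adjusted for the qualifying reading alone.

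**The case against.** The strongest reply is that the endpoint is a comparison with a concurrent randomised control, stated in section 2, 6.2 and 7.3.2, so a fall common to all arms cancels. That stands. A reader might infer that selecting on a high reading biases the estimated intervention effect; the documents do not support this, because the same selection rule applies to every arm. The fall is a matter of interpreting within-arm figures.

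Second, 7.3.2 already plans an adjusted analysis and 6.1 collects systolic BP, so baseline may end up in the model. It may, but the plan does not say so, and it ties adjustment to imbalance rather than precision.

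Third, replacing the initial value with the window mean would not cure the selection. The history is also required to be above goal, so in the Step 3 example the fall only drops from 7.4 to 4.1 mmHg. The window readings are older on average, and the eligibility rule excludes intensification only at or since the latest visit, so some may predate a regimen change. In that case the fall is hardly reduced. This stands too: the case for the mean is as a covariate, not as a cleaner starting point.

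Fourth, the sizes are soft. Patients may qualify on diastolic pressure alone and need show no systolic fall. Taking the lowest same-day reading would soften the selection. The above-goal history is not defined as a mean. The ICC is borrowed, and 180 per arm ignores the roughly 20% missing follow-up expected in 7.3.2. The last two affect the half-widths more than their ratios.

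**Conclusion.** The point holds as one of definition, interpretation and precision for a secondary endpoint of a pilot. The 6-month label does not describe the interval measured. Within-arm changes, control included, will contain an artificial fall of about 2 to 11 mmHg under the assumptions in Step 2. Raw change is less precise than a baseline-adjusted analysis: adjusting for the window mean narrows the half-width by roughly 7 to 15%, and in the worked example about 63% of the gain comes from adjustment itself. All of this rests on assumed SDs and correlations.

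A reader might also infer that the change typically spans 30 months. The documents do not support that. It is an outer bound which assumes eligibility is frozen at study start, it falls to about 24 months if lists are refreshed before visits, and no typical age of the qualifying reading can be derived.

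**What to change.** - **7.3.2:** prespecify pre-randomisation systolic BP as a covariate in the main model for this outcome, whether or not the arms are imbalanced. Use the mean of the outpatient systolic readings in the 18-month window, alone or alongside the qualifying reading. Close the window at the physician's randomisation so that the intervention cannot affect the covariate.
- **Sections 2 and 6.2:** reword the endpoint as the between-arm difference in systolic BP at the last reading within 6 months after the targeted visit, adjusted for pre-randomisation systolic BP. Keep the qualifying reading for eligibility.
- **6.2 and reporting:** state that within-arm changes include regression to the mean and are not effects. Report the distribution of the interval from qualifying reading to follow-up by arm.

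The cost is wording: eligibility already draws on the 18-month BP history, and no patient contact or change in care is involved. The downside is small. Some window readings are older or may predate a regimen change, which reduces the gain, and patients with one reading keep that reading.

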3.1 Study site

Study participants will be recruited from primary care physicians (PCPs) at Massachusetts General Hospital (MGH). MGH is part of Mass General Brigham (MGB), a large integrated delivery network in Boston, MA.

3.2 Overall design

We propose a pragmatic randomized controlled trial to test two interventions targeting clinical inertia in hypertension compared to control, followed by predictive modeling to identify factors that are associated with intervention responsiveness.

For Aim 1, we will use Electronic Health Record (EHR) data to identify physicians of patients whose hypertension treatment was not intensified despite their having persistently elevated blood pressure. We will then randomize primary care physicians to one of three arms: academic e-detailing, social norming, or no intervention (control).

For Aim 2, we will conduct interviews with select physicians from each arm. We will then identify patient and physician characteristics that are associated with inertia and with responsiveness to each intervention.

3.2.1 Aim 1 Design

In Aim 1 of the study, we will conduct a three-arm randomized controlled trial to compare the effectiveness of two interventions compared to control on clinical inertia in hypertension treatment. We will recruit 45 primary care physicians (PCPs) in the Mass General Hospital (MGH) system caring for patients who are potentially in need of hypertension treatment intensification.

Using EHR data, we will first identify patients: (1) aged 18-79; (2) for whom the recent blood pressure (BP) history in the last 18 months is above goal, (3) whose most recent BP at an outpatient visit was above goal, and (4) who did not have their hypertension treatment regimens intensified (dose increase, new medication added, or medication exchange) at or since that time.

The BP goal for this study will be <140/90 for all patients. If there are multiple blood pressures on the same day, we will select which BP to use for the study. This will either be the lowest BP from that day (if this is routinely available in the EDW) or the last BP measured that day (this is available in the EDW). The choice of which BP to use will be applied uniformly to all patients after reviewing preliminary data on BP availability in the EDW. To accommodate changes in care delivery that occurred during the COVID surge, outpatient visits will include in-office and virtual visits that had vitals recorded in the EHR the same day. We will exclude patients who,

based upon EHR data, are excluded from the hypertension registry, are pregnant or post-partum 6 months, or who are receiving hospice care.

In order to ensure that sufficient patient visits occur during the intervention period for Aim 1 and enough patients per physician for our prediction model development in Aim 2, primary care physicians will need to have at least 2 patients on their panel meeting these criteria to be eligible for the study. We will also exclude physicians with fewer than 100 patients on their primary care panel or who practice less than 1 session per week.

Physicians will be informed about the study and agree to participate using an online consent process through RedCap, and then will be asked to complete a set of behavioral surveys administered through RedCap. PCPs will then be randomized to one of the two intervention arms or control arm. To minimize imbalance between treatment groups, we will use block stratified randomization. Based on the number of sessions per week, providers will be determined to have a small (1-2 sessions), medium (3-4 sessions), or large (5 or more sessions) panel. Within each stratum, we will array physicians into blocks of 3 (note: could also be multiples of 3). All possible balanced combinations of assignment within the block will be allowed in each stratum. Ultimately, within each block and each stratum, physicians will have an equal probability of being assigned to one of the 3 arms.

